8.2.2 Suspected Unexpected Serious Adverse Reaction

A suspected unexpected serious adverse reaction (SUSAR) is defined as any serious adverse reaction, for which the nature, severity or outcome is not consistent with the applicable drug information (e.g. IB for an unapproved investigational product or package insert/summary of product characteristics for an approved product).

The reference document for assessment of expectedness in this study will be the pembrolizumab IB.

The assessment of expected / unexpected character is the responsibility of the sponsor.

New event: is defined as any new event relating to the conduct of the trial or the development of the investigational medicinal product where that new event is likely to affect the safety of the subjects.

8.2.3 Serious Adverse Event Reporting

The investigator ensures that adequate medical care is provided to the patient. Treatment of the event may require decoding of the IP.

The investigator must immediately and no later than 24 hours following knowledge of the event, notifies the R&D UNICANCER pharmacovigilance unit of any SAE or any new event defined here above, whether or not related to the research, which occurs during the 'trial reporting period'. This reporting period:

- Starts at the date of the signature of the informed consent form,
- covers the entire period during which the patient is receiving the IP or is subject to specific procedures related to the trial,
- covers a period of 100 days after the last administration of the experimental drug.

Any later SAE, i.e. occurring after a period of 100 days, which is considered to be related to the IP or to the research (other treatment used, diagnostic procedures and examinations carried out during the research) must be reported without any limitation in terms of deadline.

Notification must be made immediately by fax to the R&D UNICANCER pharmacovigilance unit by sending the form "notification of an SAE", located in the Investigator Master File, completed as precisely as possible, dated and signed by the physician-investigator:

Notification must be carried out immediately by fax to the R&D UNICANCER pharmacovigilance unit:

R&D UNICANCER

Pharmacovigilance unit, France
[contact] – [contact]
Email: [contact]

The R & D UNICANCER pharmacovigilance unit will inform Merck Global Safety ([contact]) and other appropriate persons about all SAEs, as well as pregnancy and events of clinical interest (see Section 8.3), within 2 working days of knowledge of the event.

Abnormal laboratory results should be reported as SAE if they possibly put at risk the patient or they require medical intervention to prevent an outcome corresponding to one of severity criteria.

Second cancers, whether or not related to the research, must be reported to the R&D UNICANCER pharmacovigilance unit without any limitation in terms of deadline.

The Investigator **shall send additional information to the R&D UNICANCER pharmacovigilance unit** using a SAE declaration form (by ticking the Follow-up X box to specify that it is a follow-up and not an initial report) as soon as he is aware of the event. He shall also submit the last follow-up at the resolution or stabilization of the SAE.

The Investigator is responsible for appropriate medical follow-up of patients until the resolution or stabilization of the event or until the death of the patient. This can sometimes mean that the follow-up continues after the patient has left the trial.

The Investigator must keep the documents concerning the suspected SAE in order to supplement the information previously submitted if necessary.

Requests for clarification and / or additional information may be sent to the Investigator by the R&D UNICANCER pharmacovigilance unit or Sponsor clinical research associate (CRA) of the trial to document and treat the case.

The physician-investigator should also attach to the form « notification of a SAE », whenever possible:

- a copy of the hospital report or extended hospitalization report,
- a copy of all results of additional investigations carried out, including also relevant negative results, and enclosing the normal laboratory values,
- a copy of the autopsy report if necessary,
- any other document deemed to be useful and pertinent.

All these documents must be pseudonymised.

DOC43 Protocol ME EN v1.0 05-09-2014

Overdose:

For purposes of this trial, an overdose of pembrolizumab will be defined as any dose of 1,000 mg or greater (≥5 times the indicated dose). If a dose of pembrolizumab meeting the protocol definition of overdose is taken without any associated clinical symptoms or abnormal laboratory results, the event of overdose is to be reported as a SAE, using the terminology "accidental or intentional overdose without adverse effect."

If an adverse event(s) is associated with ("results from") the overdose of IP, the adverse event(s) is to be reported as a SAE, using the terminology "EVENT due to overdose", even if no other seriousness criteria are met (Section 8.2.1).

All reports of overdose with and without an adverse event must be reported to the Sponsor immediately and no later than 24 hours following the Investigator's knowledge of the event.

Events related to disease progression:

Events occurring within the trial reporting period that meet the criteria of a SAE (Section 8.2.1) but which are related to, or occur in the context of disease progression do not require expedited reporting as described above. These events are to be considered as serious however, and should be reported as such in the CRF and followed for outcome.

Second course of pembrolizumab

For patients receiving second course of study product (see section 5.5), SAE occurred after reintroduction of the IP, pembrolizumab, must be notified to the sponsor in the same manner and timelines that the first course of pembrolizumab. SAE must be reported since the first administration of the second course of pembrolizumab, during entire period which the patient is receiving the IP and until a period of 100 days after its last administration.

SAE occurring after this period of 100 days, which is considered to be related to the IP or to the research, must be reported without any limitation in terms of deadline. It is agreed that the second course of pembrolizumab, as part of this clinical trial, will not exceed 12 months.

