1.1.3.3 Pharmacokinetic and Pharmacodynamic Data

Pharmacokinetic (PK) data analysis of pembrolizumab administered Q2W and Q3W showed slow systemic clearance, limited volume of distribution, and a long half-life (refer to the IB for details). Pharmacodynamic data (IL-2 release assay) suggested that peripheral target engagement is durable (>21 days). This early PK and pharmacodynamic data provides scientific rationale for testing a Q2W and Q3W dosing schedule.

A population PK analysis has been performed using serum concentration time data from 476 patients. Within the resulting population PK model, clearance and volume parameters of pembrolizumab were found to be dependent on body weight. The relationship between clearance and body weight, with an

allometric exponent of 0.59, is within the range observed for other antibodies and would support both body weight normalized dosing or a fixed dose across all body weights. Pembrolizumab has been found to have a wide therapeutic range based on the melanoma indication. The differences in exposure for a 200 mg fixed dose regimen relative to a 2 mg/kg Q3W body weight based regimen are anticipated to remain well within the established exposure margins of 0.5 – 5.0 for pembrolizumab in the melanoma indication. The exposure margins are based on the notion of similar efficacy and safety in melanoma at 10 mg/kg Q3W vs. the proposed dose regimen of 2 mg/kg Q3W (i.e. 5-fold higher dose and exposure). The population PK evaluation revealed that there was no significant impact of tumour burden on exposure. In addition, exposure was similar between the NSCLC and melanoma indications. Therefore, there are no anticipated changes in exposure between different indication settings.

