1.2 International Non-Proprietary Name and Description of Investigational **Products**

This trial protocol intends to evaluate the efficacy and safety of pembrolizumab (MK-3475).

Pembrolizumab is a potent humanized IgG4 mAb with high specificity of binding to the PD-1 receptor, thus inhibiting its interaction with its ligands PD-L1 and PD-L2.

Pembrolizumab is approved for use by the European Medicines Agency for treatment of the following indications:

- Advanced (unresectable or metastatic) melanoma in adults.
- Locally advanced or metastatic NSCLC in adults whose tumours express PD-L1 and who have received at least one prior chemotherapy regimen. Patients with EGFR or ALK positive tumour mutations should also have received approved therapy for these mutations prior to receiving pembrolizumab.

In the United States of America pembrolizumab has received accelerated approval from the Food and Drug Administration (FDA) for use the following indications:

Patients with unresectable or metastatic melanoma.

Protocol n° UC-0105/1612 - version n°10.0, November 22, 2021

- Patients with metastatic NSCLC whose tumours have high PD-L1 expression [(Tumour Proportion Score (TPS) ≥50%)] as determined by an FDA-approved test, with no EGFR or ALK genomic tumour aberrations, and no prior systemic chemotherapy treatment for metastatic NSCLC.
- Patients with metastatic NSCLC whose tumours express PD-L1 (TPS ≥1%) as determined by an FDA-approved test, with disease progression on or after platinum-containing chemotherapy.
 Patients with EGFR or ALK genomic tumour aberrations should have disease progression on FDA-approved therapy for these aberrations prior to receiving pembrolizumab.
- Patients with recurrent or metastatic Head and Neck squamous cell carcinoma (HNSCC) with disease progression on or after platinum-containing chemotherapy.

Posology

The recommended dose of pembrolizumab is 200 mg administered intravenously over 30 minutes every 3 weeks. Treatment should be continued as long as clinical benefit is observed or until treatment is no longer tolerated by the patient.

Dose escalation or reduction is not recommended. Dosing delay or discontinuation may be required based on individual safety and tolerability.

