 - Trophoblastic germ-cell tumour progressing after standard therapy.
 - Natural killer T-cell lymphoma: extranodal NK/T-cell lymphoma regardless of localization that is resistant or refractory to prior L-asparaginase therapy.
- 3. Metastatic disease or unresectable locally advanced malignancy that is resistant or refractory to standard therapy or for which standard therapy does not exist or is not considered appropriate by the Investigator.
- 4. Aged ≥ 18 years old for cohort 2 to 7 and aged ≥ 15 years old for patients included in cohort 1 (rare sarcoma).
- 5. Measurable disease defined:
 - according to RECIST v1.1 guidelines (Eisenhauer, 2009) for patients with solid tumours;
 - according to IPCG response criteria (Abrey, 2005) for patients with PCNSL;
 - according to RECIST v1.1 and / or abnormal levels of AFP, hCG and LDH for patients with germ-cell cancer;

- as focal uptake in at least one nodal or extra-nodal site with a Lugano 5-PS score of 4 or 5 (Cheson, 2014) for patients with NK/T-cell lymphoma,
- 6. Able to provide a FFPE biopsy sample of a metastatic site or primitive tumour tissue.

Note: Patients for whom suitable archived biopsy material is not available must be willing to undergo a biopsy of a tumour lesion prior to study entry, unless this is medically contraindicated (e.g. site inaccessible or patient safety concerns).

- 7. Patients must have a mandatory treatment-free interval of at least 21 days following previous systemic anti-cancer treatments.
- 8. Patients who have received previous systemic anticancer treatment and/or radiotherapy should have recovered from any treatment related toxicity, to a level of ≤ grade 1 (according to NCI-CTCAE criteria, v 4.0, Appendix 5) with the exception of Grade 2 alopecia.
- 9. Adequate hematologic function (absolute neutrophil count [ANC] \geq 1.0 x10⁹/L, platelets \geq 100 x10⁹/L, haemoglobin \geq 9 g/dL) measured within 14 days of treatment initiation unless due to lymphoma associated haemophagocytic lymphohistiocytosis (HLH).
- 10. Adequate renal function (creatinine clearance ≥ 50 mL/min using the MDRD or CKD EPI method) measured within 14 days of treatment initiation.
- 11. Adequate hepatic function (serum bilirubin ≤ 1.5 x the reference upper limit of normal (ULN) unless due to Gilbert's syndrome; ASAT and ALAT ≤ 3 xULN) measured within 14 days of treatment initiation unless due to lymphoma associated HLH. For patients with documented liver metastasis ASAT/ALAT ≤ 5x ULN is acceptable.

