5.2 Therapeutic Scheme

Pembrolizumab will be administered by intravenous infusion over 30 minutes at a dose of 200 mg in adult patients, or at a dose of 2mg/kg (maximum dose 200 mg) for patients 15-17 years old, on Day 1 of every 21-day cycle. Every effort should be made to target infusion timing to be as close to 30 minutes as possible; given the variability of infusion pumps from site to site however, a window of -5 minutes and +10 minutes is permitted (i.e., infusion time is 30 minutes: -5 min/+10 min).

The Pharmacy Manual contains specific instructions for the preparation of the pembrolizumab infusion fluid and administration of infusion solution.

Treatment should be continued as long as clinical benefit is observed or until treatment is no longer tolerated by the patient (Section 3.6) up to a maximum of 24 months (or 35 cycles, whichever is longer).

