5.10 Rescue Medication

5.10.1 Supportive Care Guidelines

Subjects should receive appropriate supportive care measures as deemed necessary by the treating Investigator. Suggested supportive care measures for the management of AEs with potential immunologic etiology are outlined in Table 3 (Section 5.3). Where appropriate, these guidelines include the use of oral or intravenous treatment with corticosteroids as well as additional anti-inflammatory agents if symptoms do not improve with administration of corticosteroids.

Note that several courses of steroid tapering may be necessary as symptoms may worsen when the steroid dose is decreased. For each disorder, attempts should be made to rule out other causes such as metastatic disease or bacterial or viral infection, which might require additional supportive care. It may be necessary to perform conditional procedures such as bronchoscopy, endoscopy, or skin photography as part of evaluation of the event. The treatment guidelines are intended to be applied when the Investigator determines the events to be related to pembrolizumab. If after the evaluation the event is determined not to be related, the Investigator does not need to follow the treatment guidance below.

Management of Infusion Reactions:

Signs and symptoms usually develop during or shortly after drug infusion and generally resolve completely within 24 hours of completion of infusion. Table 4 below shows treatment guidelines for subjects who experience an infusion reaction associated with administration of pembrolizumab.

Overdose:

For purposes of this trial, an overdose of pembrolizumab will be defined as any dose of 1,000 mg or greater (≥5 times the indicated dose). No specific information is available on the treatment of overdose of pembrolizumab. Appropriate supportive treatment should be provided if clinically indicated. In the event of overdose, the subject should be observed closely for signs of toxicity. Appropriate supportive treatment should be provided if clinically indicated.

Table 4. **Infusion Reaction Treatment Guidelines**

Grade ⁽¹⁾	Treatment	Premedication at subsequent dosing
Grade 1 Mild reaction; infusion interruption not indicated; intervention not indicated	Increase monitoring of vital signs as medically indicated until the patient is deemed medically stable in the opinion of the investigator.	None

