8.2 Serious Adverse Events

8.2.1 General definition

A serious adverse event is defined as any untoward medical occurrence or effect that at any dose:

- results in death,
- is life-threatening,
- requires hospitalization or prolongation of existing hospitalization,
- results in persistent or significant disability or incapacity,
- is a congenital anomaly or birth effect,
- or is medically relevant in the context of the pathology and the clinical trial.

These characteristics/consequences have to be considered at the time of the event. For example, regarding a life-threatening event, this refers to an event in which the subject was at risk of death at the time of the event; it does not refer to an event which hypothetically might have caused death if it was more severe.

The terms disability and incapacity correspond to any clinically relevant physical or psychic handicap, transient or permanent, with impacts on the physical condition/activity and/or the quality of life of the patient.

Medical and scientific judgment should be exercised in deciding whether other situations should be considered serious, such as important medical events that might not be immediately life-threatening or result in death or hospitalization, but might jeopardize the patient or might require intervention to prevent one of the other outcomes listed in the definition above (for example: overdose, second cancer,...).

The following events leading to a hospitalization or prolongation of hospitalization are not considered as Serious Adverse Events:

- Hospitalisation already scheduled before the start of the trial,
- Hospitalisation required as part of the protocol (biopsy, chemotherapy, etc.),

Any SAE, or follow up to a serious adverse event (including death due to any cause other than progression of the cancer under study) that occurs from the time the informed consent form is signed until 28 days after the last dose of IP must be reported to the Sponsor within 24 hours of the Investigator's knowledge.

Additionally, any SAE which is considered to be related to the study treatment by an investigator which occurs at any time outside of the time period specified in the previous paragraph also must be reported immediately to the Sponsor.

All subjects with serious adverse events must be followed up for outcome.

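### The single 1,000 mg overdose threshold ignores the 2 mg/kg regimen at ages 15-17, so below 100 kg automatic overdose reporting starts above 5-fold

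*Protocol*

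**What the plan says.** The overdose definition appears in Section 5.10.1 (Supportive Care Guidelines) and again, in the same words, in Section 8.2.3 (Serious Adverse Event Reporting): "an overdose of pembrolizumab will be defined as any dose of 1,000 mg or greater (≥5 times the indicated dose"). Neither place gives a version by age or by weight.

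Two consequences follow from meeting the definition:

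- Section 5.10.1: "In the event of overdose, the subject should be observed closely for signs of toxicity".
- Section 8.2.3: an overdose without symptoms or abnormal laboratory results is still reported as a serious adverse event, and "All reports of overdose with and without an adverse event must be reported to the Sponsor immediately and no later than 24 hours" after the investigator learns of it.

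The protocol has two indicated doses. Section 1.2, under Posology, names only one: "The recommended dose of pembrolizumab is 200 mg administered intravenously over 30 minutes every 3 weeks". Section 5.2 gives adults that same 200 mg but sets the dose for minors "at a dose of 2mg/kg (maximum dose 200 mg) for patients 15-17 years old". Minors are eligible through inclusion criterion 4 in Section 4.1: "aged ≥ 15 years old for patients included in cohort 1 (rare sarcoma").

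**The concern.** The yardstick in the definition is a multiple of the indicated dose, and the milligram figure attached to it fits only the 200 mg regimen. The dosing text carries the adolescent regimen and the overdose text does not.

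On the natural reading the milligram figure governs. The gloss of at least 5-fold then remains literally true for everyone, because no indicated dose exceeds 200 mg. For a patient aged 15-17 under 100 kg, however, a range of doses that are 5-fold or more falls outside the definition. If the parenthesis is instead read as a criterion in its own right, the two halves disagree for these patients, and two sites could classify the same dose differently.

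What is at stake is the automatic trigger. A fixed overdose definition ensures that an overdose without symptoms is reported and watched without anyone having to decide whether it matters. For lighter adolescents it does not do this until well past 5-fold.

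**Working it through.** **Inputs**

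- Overdose threshold: 1,000 mg (Sections 5.10.1 and 8.2.3).
- Indicated dose in adults: 200 mg (Section 5.2).
- Indicated dose at ages 15-17: 2 mg/kg, maximum 200 mg (Section 5.2).
- Vial size: 100 mg (Section 5.1).
- Adolescent body weight: not given in the protocol. The weights below are assumptions for illustration.

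**The plan's own figure.** Adults: 1,000 / 200 = 5.0. The stated 5-fold is reproduced exactly.

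**Ages 15-17.** With weight w in kg:

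- Indicated dose D = min(2w, 200) mg.
- The 200 mg cap is reached at 200 / 2 = 100 kg.
- Multiple of the indicated dose at the threshold = 1,000 / D. Below 100 kg this is 1,000 / (2w) = 500 / w. From 100 kg upward it is 5.0.
- Dose at which 5-fold is reached = 5D. Below 100 kg this is 10w mg, that is, 10 mg/kg at every weight.

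| Assumed weight (kg) | Indicated dose (mg) | 5-fold reached at (mg) | Vials at 5-fold | Multiple at 1,000 mg | mg/kg at 1,000 mg |
|---|---|---|---|---|---|
| 40 | 80 | 400 | 4 | 12.5 | 25.0 |
| 50 | 100 | 500 | 5 | 10.0 | 20.0 |
| 60 | 120 | 600 | 6 | 8.3 | 16.7 |
| 70 | 140 | 700 | 7 | 7.1 | 14.3 |
| 90 | 180 | 900 | 9 | 5.6 | 11.1 |
| 100 | 200 | 1,000 | 10 | 5.0 | 10.0 |

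The uncovered range runs from 10 mg/kg to just under 1,000 mg. It narrows as weight rises and closes at 100 kg. For example, 600 mg given to a 50 kg adolescent is 600 / 100 = 6-fold and is not an overdose under the milligram figure.

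**Where 10 mg/kg sits.** Section 1.1.3.3 bases its 0.5 to 5.0 exposure margin in melanoma on similar efficacy and safety at 10 mg/kg compared with "2 mg/kg Q3W (i.e. 5-fold higher dose and exposure"). So 10 mg/kg is the top of that margin, and it is also the highest dose for which the protocol reports data. Apart from its lower edge, the uncovered range lies above it.

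**The case against.** The strongest reply is that nothing in the text is false. The definition is stipulated for this trial, 1,000 mg is at least five times every indicated dose, and if the parenthesis is taken as the criterion the gap disappears. This stands as to literal truth. It does not supply a threshold for adolescents, and either reading needs clearer wording.

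Second, reporting is not lost. Section 8.2.1 allows as serious an important medical event that "might require intervention to prevent one of the other outcomes listed in the definition above (for example: overdose, second cancer"), so overdose is named there. Section 8.2.3 requires 24-hour notice of a new event, which Section 8.2.2 ties to a likely effect on safety. Ordinary adverse event reporting (Section 8.1.3) and the duty of adequate medical care also apply. All of this stands, and it limits the point to the automatic trigger, because the 8.2.1 and 8.2.2 routes both depend on judgement.

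Third, a 50 kg adult given 1,000 mg also receives 20 mg/kg, and 10 mg/kg was given in earlier trials with safety described as similar to 2 mg/kg. This also stands: the mg/kg figures show no hazard special to adolescents, and 10 mg/kg is not a toxicity limit. But the protocol's yardstick is the multiple of the indicated dose. The adult meets it exactly at 1,000 mg and the lighter adolescent passes it much earlier.

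Fourth, the event is remote. At 50 kg it takes at least five vials where one is indicated, and Section 5.8 has drug supplied per patient. The more foreseeable mistake, giving the adult 200 mg to a 50 kg adolescent, is 200 / 100 = 2-fold, which falls below both the present trigger and any 5-fold trigger. That is why the rating is minor.

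**Conclusion.** The point holds and is minor. For patients aged 15-17 under 100 kg, the automatic overdose report and the close-observation instruction begin at 500 / weight times the indicated dose instead of at 5-fold, and no other section of the protocol gives an adolescent threshold. The direction and the 100 kg limit follow from the protocol's own doses. The sizes quoted (12.5-fold at 40 kg down to 5.6-fold at 90 kg) rest on assumed weights and on reading the milligram figure as governing.

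The practical effect is very small. It concerns only large dosing errors in a few cohort 1 patients, and mainly those without symptoms. No efficacy endpoint, stopping rule, sample size or dosing instruction depends on it.

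**What to change.** In both Section 5.10.1 and Section 8.2.3, replace the definition with wording such as:

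> An overdose is any dose at least 5 times the patient's indicated dose under Section 5.2, i.e. 1,000 mg or greater in adults and, in patients aged 15-17, a dose at or above the lower of 10 mg/kg and 1,000 mg.

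This gives 400, 500, 600, 700 and 900 mg at 40, 50, 60, 70 and 90 kg, and 1,000 mg from 100 kg upward. The adult rule does not change.

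The cost is one sentence in each of two sections at the next amendment, an update to the guidance for the serious adverse event form, and at most a few extra overdose reports. One anomaly has to be accepted: at 50 kg, a 17-year-old would trigger at 500 mg and an adult at 1,000 mg. That follows from their different indicated doses (100 mg and 200 mg).

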The median time to onset of hypophysitis was 3.5 months (range 1 day to 7.2 months). The median duration was 2.0 months (range 0.4 months to 12.7 months). Hypophysitis led to discontinuation of pembrolizumab in 4 (0.2%) patients. Hypophysitis resolved in 7 patients.

The median time to onset of hyperthyroidism was 1.4 months (range 1 day to 21.9 months). The median duration was 1.8 months (range 1 day to 12.8 months). Hyperthyroidism led to discontinuation of pembrolizumab in 2 (0.1%) patients. Hyperthyroidism resolved in 42 subjects.

The median time to onset of hypothyroidism was 3.5 months (range 0.7 weeks to 18.9 months). The median duration was 5.5 months (range 0.9 weeks to 24.3 months). No patients discontinued pembrolizumab due to hypothyroidism.

Pneumonitis

The median time to onset of pneumonitis was 3.1 months (range 2 days to 19.3 months). The median duration was 1.6 months (range 0.3 weeks to 15.1 months). Pneumonitis led to discontinuation of pembrolizumab in 21 (1.0%) patients. Pneumonitis resolved in 32 patients.

Colitis

The median time to onset of colitis was 3.0 months (range 1.3 weeks to 9.7 months). The median duration was 1.2 months (range 1 day to 7.2 months). Colitis led to discontinuation of pembrolizumab in 15 (0.7%) patients. Colitis resolved in 31 patients.

Hepatitis

The median time to onset of hepatitis was 0.8 months (range 1.1 weeks to 21.4 months). The median duration was 1.2 months (range 1.1 weeks to 4.7 months). Hepatitis led to discontinuation of pembrolizumab in 6 (0.3%) patients. Hepatitis resolved in 14 patients.

Nephritis

The median time to onset of nephritis was 5.1 months (range 1.7 weeks to 12.8 months). The median duration was 1.1 months (range 0.4 months to 3.3 months). Nephritis led to discontinuation of pembrolizumab in 2 (0.1%) patients. Nephritis resolved in 4 patients.

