7.2.8.1 Disease Progression: Special Considerations for First Disease Evaluation

In some patients, immune-related response patterns can be characterized by an initial increase in size of tumour lesions before any subsequent decrease in tumour burden. In order to avoid prematurely interrupting the patients' treatment, the following guidelines should be observed.

At the first disease evaluation only (i.e. Day 84, \pm 7 days): In the event that the patient shows an increase in lesion size consistent with RECIST v1.1 or IPCG criteria for disease progression, the investigator may also consider the signs of clinical deterioration when deciding how to manage the situation:

- If the patient presents with signs and symptoms that could be related to disease progression: the patient is to be considered as having progressive disease and is to be withdrawn from treatment
- If the patient presents no clinical signs or symptoms associated with disease progression and the investigator suspects an immune-related response: treatment may be continued at the investigators discretion. In this case a follow-up clinical and radiological assessment performed within 28 days (± 7 days). If at this follow-up assessment the disease is evaluated as stable or responding according to RECIST v1.1 or IPCG response criteria, treatment may be continued and the patient will remain on study. If radiological disease progression is confirmed by this second evaluation however, the treatment will be discontinued (regardless of clinical status) and the appropriate end of treatment evaluations performed.

For the purposes of analysis, the results of both the initial (Day 84) disease assessment and follow-up disease assessment should be recorded in the eCRF. In all cases, evaluation of response will be made according to RECIST criteria base on radiological measurement.

For time to event analyses, the date of disease progression will be considered as the date of the initial evaluation at which disease progression was suspected (as per RECIST / IPCG recommendations) regardless of the clinical decision taken.

If the criteria for disease progression are met at a time point later than Day 84, the patient is to be withdrawn from treatment, regardless of clinical status. No confirmation of PD is required in this case.

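### The progression exemption from 24-hour SAE reporting in Section 8.2.3 has no exception for pembrolizumab-related events and does not match Section 8.2.1 or the flow chart

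*Protocol*

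**What the plan says.** Section 8.2.3 sets the general rule. Within 24 hours of learning of the event, the investigator "notifies the R&D UNICANCER pharmacovigilance unit of any SAE or any new event defined here above, whether or not related to the research". The reporting period starts at consent and "covers a period of 100 days after the last administration of the experimental drug"; later SAEs stay reportable, without time limit, if they are related.

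Further down, under a run-in heading on events related to progression, the same section takes up events inside that period that meet the SAE criteria "but which are related to, or occur in the context of disease progression do not require expedited reporting as described above". What remains for them is this: "These events are to be considered as serious however, and should be reported as such in the CRF and followed for outcome".

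Section 8.2.1 has its own rule. Any SAE from consent to 28 days after the last dose goes to the sponsor within 24 hours, "including death due to any cause other than progression of the cancer under study". It adds that an SAE which an investigator considers treatment-related, at any time outside those 28 days, must also be reported immediately. That sentence carries no progression exemption.

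Footnote 4 of the flow chart (Synopsis, section H) asks for all SAEs up to 100 days after the last dose, and related ones after that. It does not mention progression.

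**The concern.** The exemption joins two limbs with an 'or'. Being related to progression already covers events caused by it, so the alternative must add something, and what it adds is circumstance without cause. No words bring pembrolizumab-related events back into the 24-hour route. An investigator who sees a serious immune-mediated event in a patient whose disease is progressing could enter it in the CRF and send no notification, and would be following the text.

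Two steps depend on the notification. Expectedness is the sponsor's judgement (Section 8.2.2). The pharmacovigilance unit passes SAEs to the licence holder within 2 working days of knowing of them (Section 8.2.3). Neither can start until the sponsor knows. Section 13.1 asks only that CRF data be entered in a timely manner and gives no number of days, so the protocol puts no limit on the delay.

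**Working it through.** No power or error-rate calculation applies. The check sets the rules side by side for one case: an SAE judged related to pembrolizumab, inside the reporting period, in a patient who has progressed.

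| Place | What it requires for this event |
|---|---|
| 8.2.1, up to 28 days after last dose | 24-hour report; only death from progression is left out |
| 8.2.1, after 28 days | Immediate report, because it is related |
| Flow-chart footnote 4 | Report, up to 100 days; no exemption |
| 8.2.3, general rule | 24-hour notification |
| 8.2.3, exemption, second limb read literally | CRF entry and follow-up only |

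Footnote 4 gives no 24-hour limit. It says that late related events must also go to the sponsor's safety office, which implies that the earlier ones do too.

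How much time the conflict covers, in one worked case. Inputs: 21-day cycles, so Cycle 4 Day 1 is Day 64 (flow chart); first disease assessment at Day 84 (Section 7.2.8); windows of 28 and 100 days (Sections 8.2.1 and 8.2.3). Assumption: the last dose is on Day 64 and progression is found on Day 84.

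- End of the 8.2.1 window: 64 + 28 = Day 92.
- End of the 8.2.3 window: 64 + 100 = Day 164.
- Days after progression inside the 8.2.3 window: 164 − 84 = 80.
- Of these, under the any-SAE rule of 8.2.1: 92 − 84 = 8.
- Of these, under the related-SAE rule of 8.2.1: 164 − 92 = 72.

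Since 8 + 72 = 80, Section 8.2.1 asks for prompt reporting of a related SAE (other than death from progression) on every one of these days, while the literal exemption in 8.2.3 allows CRF entry on every one. As an example, Section 1.1.3.2 states: "The median time to onset of pneumonitis was 3.1 months". At 30.4 days per month that is 3.1 × 30.4 ≈ Day 94, in the 72-day stretch. A serious, related pneumonitis on that day is reported immediately under one section and may go to the CRF only under the other.

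Two comparisons inside the protocol suggest that this was not intended:

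- A related SAE on post-dose day 101 must be reported. The same event on day 99 in a progressing patient may be exempt.
- A hepatic event of clinical interest that is not serious goes to the sponsor within 24 hours with no progression exemption (Section 8.3). A serious immune-mediated event in a progressing patient may not.

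**The case against.** The strongest reply is that the paragraph's heading speaks of events related to progression. Under it, the second limb can reasonably mean complications of progression. A pneumonitis that the investigator attributes to pembrolizumab is not naturally such an event. This stands as a possible reading, so the defect is ambiguous wording and not a declared exemption of drug-related SAEs. It does not remove the defect, because the separate causal limb makes the wider reading at least as natural.

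Second, 8.2.1 and footnote 4 still call for these reports. That is true, and in the worked case 8.2.1 reaches all 80 days for related SAEs. But sites then hold two conflicting instructions, and the permissive one is in the section titled for SAE reporting.

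Third, exempted events stay serious, are recorded in the CRF and are followed for outcome. This stands, and it limits the harm to delay.

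A reader might also infer that 8.2.3 contradicts its own opening. It does not: the exemption refers back to the rule and is an explicit exception to it. Nor is it clear that patients kept on drug past Day 84 under Section 7.2.8.1 are caught. The reason given there is that "immune-related response patterns can be characterized by an initial increase in size of tumour lesions", and continuation requires no clinical signs of progression and a suspected immune-related response. An investigator holding that view has little basis for filing an SAE under progression.

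**Conclusion.** The concern holds as a wording defect that should be fixed. As written, 8.2.3 can move a drug-related SAE in a progressing patient out of 24-hour notification. It does not match 8.2.1 or footnote 4, and the 28-day and 100-day windows also disagree. The conclusion rests on the text alone.

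The number of events affected is unknown, because the protocol gives no expected progression rate and no rate of serious events after progression. Three stronger inferences are tempting and unsupported:

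- That about half of the reporting window is exposed. In the worked case 80/164 = 49%, but with progression at the second, third or fourth assessment it is 80/248 = 32%, 80/332 = 24% and 80/416 = 19%.
- That patient counts follow from Table 1. The all-grade pneumonitis rate gives 350 × 2.4% ≈ 8, but those are not all serious and not all after progression. Grades 3 to 5 come to about 0.7–0.8%, or 2–3 of 350, before any restriction to progressing patients. The colitis row cannot be used: Grades 2 to 4 sum to 0.4 + 1.7 + 0.1 = 2.2%, above its all-grade 1.7%.
- That safety signals would be missed. CRF capture and follow-up remain, and Sections 11.2 and 11.3 describe committee reviews based on safety reports prepared by the sponsor, without tying these to the 24-hour form.

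**What to change.** In Section 8.2.3:

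- Delete the second limb of the exemption.
- Limit the exemption to events that the investigator attributes to progression of the cancer under study and judges not related to pembrolizumab.
- State that an SAE with a possible or uncertain relationship to pembrolizumab stays under 24-hour notification even when progression is present.

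Then reconcile Section 8.2.1, both parts of Section 8.2.3 and flow-chart footnote 4, so that they give one progression exception and one reporting window. The second-course paragraph of 8.2.3 applies the first-course terms and so needs no separate rule.

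The cost is a few sentences, matching instructions on the SAE form, and a modest number of additional expedited forms. Endpoints, analyses and patient management do not change.
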